## **3 Study Design**

### **3.1 General Design**

This is a multi center open-label pilot clinical trial of patients with TRE, ages 2 to 50 years old, with TSC or FCD who are scheduled for epilepsy surgery. Patients will be treated with everolimus for 7 to 21 days prior to epilepsy surgery with extension of time from 7 to 21 days in successive cohorts of patients. The initial cohort of at least three patients will be treated for 7 days and after the safety of therapy is assured for this group, there will be an extension of the treatment to 14 days for at least three patients. This will be extended at one week intervals/three patient groups to a maximum treatment duration of 21 days. Resected brain tissue will be analyzed for activation of mTORC1 and mTORC2 signaling pathways, glutamatergic and GABA-ergic neurotransmission using histochemistry, genetic analysis, as well as extracellular field recordings in acute ex-vivo brain slices from surgery. A blood sample, collected at the time of surgery, will be analyzed for everolimus levels and VEGF-D. All patients will undergo standardized intra-operative ECoG recordings over the primary epileptogenic region and reviewed blindly.

Subjects will be in the study for approximately 10 weeks. We will study variables listed in specific aims 1 and 2 in TSC and FCD patients treated with 7 to 21 days of everolimus and compare these to untreated control patients with TRE and TSC or FCD. A concurrent comparison group of 12 subjects will also be enrolled. They will all be undergoing routine surgery for the diagnosis of TRE with TSC or FCD.

All study procedures will be performed at either the Comprehensive Epilepsy Center (CEC) with the exception of the surgery, which will be performed at Tisch Hospital

CONFIDENTIAL

This document and information is the property of the NYU School of Medicine and Langone Medical Center. Do not disclose or use except as authorized in writing by the study IND sponsor

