### **5.2 Treatment Regimen**

Everolimus will be self-administered (by the patient or parent at home during the 7-21 days prior to neurosurgery). The investigator will instruct the patient to take the study drug exactly as specified in the protocol.

Patients who are eligible for the active treatment group with TSC or FCD only will receive everolimus. After a minimum of three patients are treated for 7 days (Table 2), if there is no evidence of serious adverse effects or other dose-level tolerability and safety issues, we will extend the treatment duration by a maximum of one week. Again, after a minimum of three patients are treated for two weeks without evidence of serious adverse effects or other dose-level tolerability and safety issues, we will extend the treatment duration to three weeks. For patients treated longer than two weeks, an everolimus blood level will be obtained after 10-12 days and used to adjust dose to maintain a serum level of 5-10 ug/ml. to revisit escalation and numbers. If one patient at a dose duration has a serious adverse effect during a treatment cohort period (e.g., 7 days), then up to 6 patients are treated with that dose duration. If there are 2 or more serious adverse events among the 6 patients, then the duration is dropped back to the prior level. If there are no events in 3 patients or 1 event in 6 patients, then the dose duration is escalated to the next level. At the 3 week dose duration, 6 patients will be treated even if there are no events among the first 3 patients.

Table 2: Dosing Escalation for Serial Cohorts

Serial Cohort Number	Minimum # of patients if no Grade 3 or 4 adverse event or serious adverse events	Minimum # of patients if one Grade 3 or 4 adverse event or serious adverse events ^	Duration of everolimus therapy	Result of one serious adverse events including wound healing problem and serious infection	Result of two serious adverse events including wound healing problem and serious infection
1	3	9	7 days		
2	3	6	14 days	Add additional patients to Cohort 1	Return to cohort one, no potential for longer treatment duration
3	1-3	6	21 days	Add additional patients to Cohort 2	Return to cohort two, no potential for longer treatment duration

^ Adverse events as defined by CTAE v.4.0

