#### **7.3 Subject Population(s) for Analysis**

All patients who receive one or more doses of drug will be included in the analyses of safety. Those patients who undergo surgery will be included in the analyses of S6 phosphorylation and other measurements obtained at the time of surgery. Additional analyses will be conducted to compare those subjects who did not complete treatment and surgery with respect to disease and patient characteristics to identify any potential differences between these groups of patients.

7. Sample size considerations. For this preliminary study, safety analyses are primary. Study termination will occur if, among the 9 treated subjects, there are two cases of wound healing problems or three cases of serious infection, including wound site infection. In the case of a wound site infection, any problems with wound healing will be considered secondary to the infection and NOT as a primary wound healing problem. These estimates are based on neurosurgical experience and reports with the frequency of wound healing problems of <2% and infection from 1.6 to 8.6% in six published series, with a mean infection rate of 5.3%. [33-38]

For the analysis of S6 phosphorylation, based on a 2 sample 2 sided t-test, we can detect a difference of  $|1.4| - |1.5|$  standard deviations between the comparison controls and the treated group with 9 treated subjects with alpha = 0.05 and power of 80%. Preliminary data using quantitative Western blots obtained from 4 resected tubers demonstrated phospho-S6/S6 ratios of 257 ± 42% of control. With 9 treated subjects, and 12 controls, we would be able to detect a 62 – 65% difference in phospho-S6/S6 levels between treated and untreated groups, which is likely a biologically meaningful difference. Prior studies in murine models of TSC treated with rapamycin have demonstrated 90% reduction in phospho-S6 levels [ref]

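### The duration rule in Section 5.2 has no executable consequence for two or more serious events at 7 days, and after one event at 14 or 21 days Table 2 conflicts with the prose and with itself

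*Combined protocol and SAP*

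**What the plan says.** Section 3.1 fixes the starting level: "The initial cohort of at least three patients will be treated for 7 days". Later cohorts go to 14 and then 21 days.

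The prose of Section 5.2 gives the decision rule:

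- After one serious event at a duration, "then up to 6 patients are treated with that dose duration".
- For escalation: "If there are no events in 3 patients or 1 event in 6 patients, then the dose duration is escalated to the next level".
- For failure: "If there are 2 or more serious adverse events among the 6 patients, then the duration is dropped back to the prior level".
- At three weeks, six patients are treated even if the first three have no event.

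Table 2, in the same section, restates the rule by cohort. Its minimum-patients column after one event (Grade 3 or 4, or serious) gives 9, 6 and 6 for 7, 14 and 21 days. Its result column for one serious event says "Add additional patients to Cohort 1" in the 14-day row and "Add additional patients to Cohort 2" in the 21-day row. For two events, both of those rows go back one cohort. The two result cells for Cohort 1 are blank in the text available for this review.

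Study termination is a separate rule. It applies if, among the 9 treated subjects, "there are two cases of wound healing problems or three cases of serious infection, including wound site infection" (sample size considerations under Section 7.3; repeated in the Data Safety Monitoring Plan in Section 7.1).

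**The concern.** A duration-escalation rule should tell the team, for each level and each event count, what happens to the next patient. Here the first level has no answer for the outcome the rule is meant to catch. At the second and third levels, two parts of one section give different answers after a single event.

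The plan calls safety its primary analysis, and Section 1.4 says the surgical risk of this pre-operative regimen has not been documented. The rule determines how many patients are exposed and for how long. It also decides who falls into each duration cohort, and Section 6.1 summarises both safety and S6 phosphorylation by those cohorts.

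**Working it through.** The plan states no operating characteristics for this rule, so there is no figure to reproduce. The check has three parts: each branch, the cohort sizes, and the chance of reaching the undefined branch.

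**Branches**

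| Level | Events | Section 5.2 prose | Table 2, minimum patients | Table 2, result column |
|---|---|---|---|---|
| 7 days | 1 | same duration, up to 6 | 9 | blank in supplied text |
| 7 days | 2 or more | prior level (none exists) | – | blank in supplied text |
| 14 days | 1 | same duration, up to 6 | 6 | add to Cohort 1 (7 days) |
| 14 days | 2 or more | back to 7 days | – | back to Cohort 1 |
| 21 days | 1 | same duration, up to 6 | 6 | add to Cohort 2 (14 days) |
| 21 days | 2 or more | back to 14 days | – | back to Cohort 2 |

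Two rows fail. At 7 days with two or more events, the instruction has no target. At 14 or 21 days with one event, the result column differs from the prose and from the minimum-patients column beside it.

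Take 3 patients at 7 days without an event, then one event among the first 3 at 14 days. Of 9 planned, 9 − 3 − 3 = 3 remain. They go to 14 days under the prose and to 7 days under the result column.

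**Cohort sizes**

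- No events, prose: 3 + 3 + 6 = 12, against 9 treated.
- No events, Table 2 (1–3 patients at 21 days): 3 + 3 + 1 = 7 to 3 + 3 + 3 = 9, which fits.
- One event at 7 days: up to 6 in the prose, at least 9 in Table 2, which is the whole treated group.

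**Chance that the 7-day level meets the failure criterion**

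Let *p* be the per-patient risk of a serious event. This is an assumption, shown as a range, with patients taken as independent. Three patients are treated first. With no events the level is passed. With one event, three more are treated. Two or more among the first three already meet the criterion. So

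P(fail) = P(≥2 of 3) + P(1 of 3) × P(≥1 of next 3).

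- *p* = 10%: 0.028 + 0.243 × 0.271 = 0.094
- *p* = 20%: 0.104 + 0.384 × 0.488 = 0.291
- *p* = 30%: 0.216 + 0.441 × 0.657 = 0.506
- *p* = 40%: 0.352 + 0.432 × 0.784 = 0.691

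For illustration with the plan's own mean infection rate of 5.3%: 0.0081 + 0.1426 × 0.1507 = 0.030.

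**Does the study-level stop close the gap?**

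It counts wound-healing problems (two) and serious infections (three). Two other serious events never count; Table 6 lists haemorrhage, pneumonitis and renal failure among the drug's known risks. Exactly two serious infections at 7 days meet the duration criterion but stay below three. That chance is P(2 of 3) + P(1 of 3) × P(1 of next 3): 2.8% at 5.3%, and 6.7% at 8.6%, the top of the plan's infection range.

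**The case against.** The best defence is that the plan has other safeguards. Under Medical Monitoring, safety data go to the DSMB after every three patients or after any possibly related serious event. Wound breakdown, dehiscence or infection counts as serious and prompts a decision on terminating the study. Sections 5.3, 6.5 and 7.1 stop treatment or participation for an affected subject. A reader might therefore object to any claim that two serious events at 7 days trigger nothing, and rightly: they trigger review. What survives is narrower. These provisions either act on one subject or call for a review without a cohort-level criterion, and the termination decision covers only wound events and infections.

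Several stronger readings are tempting but not supported.

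- A reader might infer that dosing can continue at any duration that failed. That applies only at 7 days. At 14 and 21 days one event is not a failure under the prose, and for two events prose and table agree.
- A reader might say Table 2 as a whole opposes the prose. It does not: its minimum-patients column agrees at 14 and 21 days.
- The blank Cohort 1 cells prove little, since tables may have been damaged in text extraction. The gap in the prose does not depend on them.
- The simple binomial chance of two or more events among six (11%, 34%, 58% and 77% at 10% to 40%) overstates the matter, because a level with no event in its first three patients escalates and never reaches six.

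The stakes are also bounded by size: with 9 treated, at most 6 patients remain after two events in the first three, and at most 3 after six.

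**Conclusion.** The point holds in two parts, and the text must be corrected.

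First, the rule for two or more serious events cannot be executed at 7 days, and no other provision pre-specifies a cohort-level action there for two events outside the wound and infection categories, or for exactly two serious infections.

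Second, after one event at 14 or 21 days the result column of Table 2 contradicts both the prose and the table's own minimum-patients column. In the worked case this changes the duration for 3 of 9 treated patients. The cohort sizes are inconsistent as well, with 12 patients needed against 9 planned when the prose is followed without events.

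The probability of reaching the undefined branch runs from 9.4% to 69.1% for assumed risks of 10% to 40%, and is 3.0% at the illustrative 5.3%. These figures rest on independence and on assumed rates, and they count serious events only, whereas Table 2's size columns also count Grade 3 or 4 events. The conclusion itself rests on the missing and conflicting instructions, whatever the true rate.

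**What to change.** Before the next patient is dosed, reconcile the prose of Section 5.2 with Table 2 so that:

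- the rule for two or more serious events has a consequence that can be carried out at 7 days, stated in both the prose and the Cohort 1 row;
- the prose and both Table 2 columns name the same duration for the next patients after one event at 14 and at 21 days;
- the cohort sizes agree between prose and table and fit the 9 treated patients.

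Which action, which events it covers and which duration applies are for the sponsor and the DSMC to decide; none is proposed here. The cost is rewording one paragraph and one table. The reconciliation itself needs no new procedures and no patients beyond the 9 planned.

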## Study Summary

Title	A Pilot Study to Evaluate the Effects of Everolimus on Brain mTOR activity and Cortical Hyperexcitability in Tuberous Sclerosis Complex (TSC) and Focal Cortical Dysplasia (FCD)
Short Title	Everolimus effects on brain mTOR and excitability
Protocol Number	Pending
Phase	2
Methodology	This is a multi center, open-label exploratory Phase II clinical trial of patients with treatment resistant epilepsy (TRE), ages 2 to 50 years old, with TSC or FCD who are scheduled for epilepsy surgery.
Study Duration	18 months of active recruitment
Study Center(s)	NYU Langone Medical Center;
Objectives	
Primary objectives: A pilot study to assess the:
 
1) feasibility and safety of recruiting patients into a prospective study for patients with TSC and FCD treated for 7-21 days before epilepsy surgery and 2) test the hypothesis that everolimus therapy in TSC and FCD patients with TRE will reduce mTOR signaling (reduced S6 phosphorylation) as compared to concurrent controls with TSC and FCD who did not receive Everolimus.
 
Secondary Objectives: to obtain preliminary data on the effect of everolimus therapy in TSC and FCD patients with TRE on mTOR signaling and cortical hyperexcitability by assessing 1) systemic mTOR signaling suppression (VEGF-D) pre- and post-treatment, 2) relation of S6 phosphorylation to specific genetic abnormalities, and 3) blood everolimus levels; and using historical controls to assess 4) markers of cortical hyperexcitability (glutamate and GABA receptors, levels of neuroinflammation (TNF-<math>\alpha</math>), axonal abnormalities, myelination defects), and 5) electrocorticographic (ECOG) recordings

Number of Subjects	21 total subjects study wide; 9 treated subjects (NYU CEC) and 12 controls (@ NYU CEC;)  This has been a very challenging study to recruit for and therefore our total number of enrolled patients is fewer than expected. This has to do with multiple factors, including a smaller number of eligible candidates, a smaller percentage of parents who have considered to participate, and the challenge imposed by the fact that many of the patients come from outside the NY Tristate area. Given this distance, enrollment of subjects 3-4 weeks before the surgery has not been possible, so we have shortened the length of the treatment phase.

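### The text of Section 5.2 and its Table 2 give different escalation rules after one event, and the text's count at 21 days does not fit the 9 treated patients planned

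*Combined protocol and SAP*

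**What the plan says.** The Study Summary sets the size: "21 total subjects study wide; 9 treated subjects (NYU CEC) and 12 controls". The sample size text, Section 6.5 and the monitoring plan in Section 7.1 also use 9 treated. Section 3.1 describes the escalation in threes: "This will be extended at one week intervals/three patient groups to a maximum treatment duration of 21 days".

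The text of Section 5.2 asks for at least three patients at 7 days and at least three at 14 days, each extension being allowed "if there is no evidence of serious adverse effects or other dose-level tolerability and safety issues". One serious adverse effect triggers expansion at the same duration: "during a treatment cohort period (e.g., 7 days), then up to 6 patients are treated with that dose duration". Then come the decision rules: "If there are no events in 3 patients or 1 event in 6 patients, then the dose duration is escalated to the next level", and "If there are 2 or more serious adverse events among the 6 patients, then the duration is dropped back to the prior level". For the last level the text says "At the 3 week dose duration, 6 patients will be treated even if there are no events among the first 3 patients". A drafting remark, "to revisit escalation and numbers", still stands in the same paragraph.

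Table 2, in the same section, gives minimum numbers for 7, 14 and 21 days of 3, 3 and 1-3 with no event, and 9, 6 and 6 with one event. Its result column for one serious event says to add patients to cohort 1 after an event in cohort 2, and to cohort 2 after an event in cohort 3.

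**The concern.** The protocol calls the safety analyses primary, and Section 1.4 says the surgical risk of this pre-operative treatment has never been documented. The escalation rule decides how long the next patients take an immunosuppressive drug before brain surgery. If text and table prescribe different actions on the same data, the investigators must choose between them after seeing the event. No section says which one governs. Separately, a rule that needs more patients than are planned cannot be followed to its end.

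**Working it through.** **Inputs.** Treated patients: 9 (Study Summary; sample size considerations; Sections 6.5 and 7.1). Cohort counts and actions: Section 5.2 text and Table 2. Background infection rate: mean 5.3%, range 1.6% to 8.6% (sample size considerations).

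**Step 1: patients needed to fill all levels.**
- Table 2, no event: 3+3+1 = 7 to 3+3+3 = 9. This reproduces the planned 9.
- Section 3.1, groups of three: 3+3+3 = 9. This also reproduces it.
- Section 5.2 text, no event: 3+3+6 = 12, which is 3 over.
- Section 5.2 text, one expansion: 6+3+6 = 15 or 3+6+6 = 15. Two expansions: 6+6+6 = 18.
- Table 2, one event at 21 days: 3+3+6 = 12, again 3 over.

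**Step 2: action after one event, with 9 treated.**

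| Event at | Section 5.2 text | Table 2 |
|---|---|---|
| 7 days (patients 1-3), none in 4-6 | 4-6 at 7 days, then escalate; 7-9 at 14 days | 9 in cohort 1; 4-9 all at 7 days |
| 14 days (patients 4-6) | up to 6 at 14 days; 7-9 at 14 days | count column: 6 at 14 days; result column: add patients at 7 days |
| 21 days (patients 7-9) | remaining patients at 21 days | count column: 6 at 21 days; result column: add patients at 14 days |

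In the second row, 3+6 = 9 uses every treated patient, so both columns of Table 2 cannot be followed. In the third row six patients are already used. The conflict can therefore affect at most two further patients, and only if the event is known before they start.

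For two events at 14 days, text and table agree: return to 7 days. For two serious events at 7 days, the text drops to a level below 7 days, which does not exist.

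**Step 3: how often the first two rows could arise (illustration).** Let p be the event probability per patient, independent and equal at 7 and 14 days.
- First row: exactly one event in patients 1-3 and none in 4-6 = 3p(1-p)^5.
- Second row: none in 1-3 and exactly one in 4-6 = 3p(1-p)^5.
- Sum: 6p(1-p)^5.

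Results: p = 0.016 gives 0.089; p = 0.053 gives 0.242 (0.121 for each row); p = 0.086 gives 0.329.

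This counts every post-operative infection as an event. It leaves out wound-healing problems, other serious adverse events, Grade 3 or 4 events and any drug effect.

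**The case against.** **Nine patients may be enough.** A reader might infer from the 12 that the study cannot be run with 9. The documents do not support that. Section 3.1 makes 21 days a maximum, no section requires it to be reached, and Table 2's no-event column fits 9. The 12 applies only if every level is filled. The figure of 18 treated patients left in Section 4.4.1 suggests that the six-patient sentence comes from a larger plan, but that is inference.

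**The exposure conflict is limited.** A reader might infer that any single event changes the next patient's treatment. After an event at 7 days it does not: patients 4-6 stay at 7 days under both rules, and only patients 7-9 can differ. This limit stands.

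**The 24% is not an estimate of the conflict rate.** It rests on infections alone, and Table 2's result columns speak of serious infection. Given what it counts and omits, it is neither an upper nor a lower bound.

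**Post-operative events.** The reference to a treatment cohort period might be read as excluding them. The Medical Monitoring text in Section 6.5 has all safety data reviewed after each three-patient cohort has completed the trial, so that reading fails.

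**Oversight exists.** Any serious adverse event possibly related to the study goes to the data safety monitoring board. Any wound breakdown, dehiscence or infection leads to a decision on whether to stop, and two wound-healing problems or three serious infections end the study. This largely covers two serious events at 7 days. Table 2's cohort 1 result cells read as blank, but the table may be broken in the machine-read text, so nothing is built on them. None of these provisions selects the duration for the next patients, so the one-event conflict remains.

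**Conclusion.** The inconsistency is real on the current wording. The text needs 12 treated patients to fill all levels against 9 planned. Its six-patient sentence and Table 2's one-event count of 6 for cohort 3 are the entries that do not fit. After one event, text and table lead to 14 versus 7 days (event at 7 or 14 days) or 21 versus 14 days (event at 21 days), for at most three patients. The two-event gap at 7 days is minor. The difference in event wording (serious effect in the text, Grade 3 or 4 or serious event in Table 2's count columns) is narrow, because the extension sentences also cover other tolerability and safety issues.

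The counts follow directly from the protocol. The 24% (9% to 33%) is illustrative and rests on the assumptions in the working. Because few patients are affected and the monitoring board sees the events, this is a should-fix. It does not show that 9 is the wrong number.

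**What to change.** Keep 9 treated and amend the wording.

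(a) State in the text that up to 3 patients will be treated at 21 days, and set Table 2's one-event count for cohort 3 to the patients remaining, at most 3.

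(b) Adopt one rule in both places.
- If the text's rule governs: set Table 2's one-event count for cohort 1 to 6, and remove both one-event result cells that add patients to an earlier cohort.
- If Table 2's step-back rule governs: delete from the text both the expansion to six at the same duration and the escalation after one event in six. Reword the drop-back sentence so that it no longer refers to six patients. Replace the one-event counts of 6 for cohorts 2 and 3 with numbers that match the step back and the 9 available (after an event at 14 days: 3 at 7, 3 at 14, then 3 more at 7).

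(c) For two serious adverse events at 7 days that do not meet the termination rule, pause for a decision by the monitoring board.

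(d) Use one event definition in text and table, and delete the drafting remark.

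The cost is amendment text. The downside is at most three patients at 21 days, and none if an event occurs in the first six. Under the same illustrative assumptions that has probability 1-(1-p)^6 = 28% at 5.3% (9% to 42% over 1.6% to 8.6%). Choosing the text's rule accepts that the last three patients may receive 14 days after one serious event in six at 7 days. Keeping six at 21 days would instead need at least 3 more treated patients, in a study that already reports difficulty recruiting.

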Statistical Methodology	
Sample size considerations. For this preliminary study, safety analyses are primary. Study termination will occur if, among the 9 treated subjects, there are two cases of wound healing problems or three cases of serious infection, including wound site infection. In the case of a wound site infection, any problems with wound healing will be considered secondary to the infection and NOT as a primary wound healing problem. These estimates are based on neurosurgical experience and reports with the frequency of wound healing problems of <math><2\%</math> and infection from 1.6 to 8.6% in published series, with a mean infection rate of 5.3%.
 
For the analysis of S6 phosphorylation, based on a 2 sample 2 sided t- test, we can detect a difference of <math> 1.4  -  1.5 </math> standard deviations between the comparison controls and the treated group with 9 treated subjects with alpha =0.05 and power of 80%. Preliminary data using quantitative Western blots obtained from 4 resected tubers demonstrated phospho-S6/S6 ratios of 257±42% of control. With 9 treated subjects, and 12 controls we would be able to detect a 64 – 65% difference in phospho-S6/S6 levels between treated and untreated groups, which is likely a biologically meaningful difference.

CONFIDENTIAL

This document and information is the property of the NYU School of Medicine and Langone Medical Center. Do not disclose or use except as authorized in writing by the study IND sponsor

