#### **4.4 Early Withdrawal of Subjects**

##### **4.4.1 When and How to Withdraw Subjects**

A subject may withdraw from the study due to:

- 1) Improvement in seizure activity to an extent that the patient and/or parents/legal guardians elect to forego epilepsy surgery for treatment with everolimus,
- 2) Difficult complying with protocol requirements or
- 3) A decision to withdrawal for personal reasons or adverse effects that are less severe than those that lead to mandatory discontinuation of the treatment phase.

A subject will be withdrawn from the study if any of the following are present:

- 1) The subject develops a systemic bacterial or fungal infection.
- 2) The subject develops a CTAE grade 3 or 4 (severe) event.
- 3) The patient and study will be terminated if he or she is the second case of impaired surgical wound healing or the third case of serious infection, including infection of the wound site, among the 18 everolimus-treated patients.

Given the short duration of treatment, there are no known or postulated safety concerns related to abrupt discontinuation after this duration and dosage of therapy with everolimus. Any subject who elects to withdraw from the study will be recommended to discontinue the everolimus therapy, but if they desire a tapering schedule, one will be provided with exception for those patients going forward with surgery, when everolimus will be completely discontinued prior to surgery.

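### Table 2 answers two wound-healing problems in the 14- or 21-day cohort with a shorter duration, although the plan terminates the study at that count

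*Combined protocol and SAP*

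**What the plan says.** Section 5.2 lengthens treatment from 7 to 14 to 21 days in successive small cohorts. The last column of Table 2 is headed "Result of two serious adverse events including wound healing problem and serious infection". Its entry for the 14-day cohort is "Return to cohort one, no potential for longer treatment duration" and for the 21-day cohort "Return to cohort two, no potential for longer treatment duration". Both entries keep the study running at a shorter duration. The text of 5.2 has a similar rule: "If there are 2 or more serious adverse events among the 6 patients, then the duration is dropped back to the prior level".

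A separate rule ends the study. The Study Summary says: "Study termination will occur if, among the 9 treated subjects, there are two cases of wound healing problems", or three cases of serious infection. The sample size considerations under 7.3 Subject Population(s) for Analysis repeat this, and the Data Safety Monitoring Plan in 7.1 gives the same thresholds and consequence. Section 4.4.1 says: "The patient and study will be terminated if he or she is the second case of impaired surgical wound healing". It counts among 18 treated patients where the other places count among 9, but the trigger is still the second case.

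A healing problem that accompanies a wound-site infection is not counted as a wound-healing case: "any problems with wound healing will be considered secondary to the infection and NOT as a primary wound healing problem".

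**The concern.** Wound healing is one of the two risks for which the termination rule was written. Table 2 is what staff would consult when deciding how long to treat the next patient. It names this event and tells them to carry on at a shorter duration. At the same count, the termination rule says that nobody further is dosed. Neither 5.2 nor Table 2 points to that rule, and no sentence elsewhere says which of the two comes first. At stake is whether a few more patients are given everolimus before elective brain surgery after the study's own limit has been reached.

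**Working it through.** The plan states no operating characteristic for either rule, so there is no figure to reproduce. The check compares the rules and then sizes the overlap.

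**Which events meet which rule.** Each row assumes no earlier wound-healing or infection case, except where it says otherwise.

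| Events | Two-event result of Table 2 (14- or 21-day cohort) | Termination rule |
|---|---|---|
| Two primary wound-healing problems, same cohort | Met: step back | Met: terminate |
| One wound-healing problem and one serious infection, same cohort | Met: step back | Not met |
| Two serious infections, same cohort | Met: step back | Not met (three needed) |
| Two wound-site infections with secondary healing problems, same cohort | Met: step back | Not met (counted as infections) |
| One wound-healing problem in each of two cohorts | Not met | Met: terminate |

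Only the first row gives opposite answers at a count of two. In that row both rules are always met, because two cases within a cohort are at least two among all treated patients.

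**Inputs for the size.**
- Nine treated patients (Study Summary).
- Three 7-day patients without an event, after which the 14-day cohort opens (section 5.2).
- Probability p of a primary wound-healing problem per patient. The documents give a background frequency below 2%, so p = 0.02 is the ceiling of that figure. The values 0.10 and 0.20 are assumptions, included because everolimus may raise the rate.
- Patients are independent, wound problems are the only serious adverse events, and q = 1 − p.

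**First three 14-day patients.**
- Both of the first two: p² = 0.0004 / 0.010 / 0.040. If the third is not yet dosed, 9 − 5 = 4 patients are left.
- Second event at the third patient: 2p²q = 0.00078 / 0.018 / 0.064. Then 9 − 6 = 3 are left.
- Sum, two or more of the first three: 0.00118 / 0.028 / 0.104, that is 0.12% / 2.8% / 10.4%.

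**Later 14-day patients.** The text of 5.2 allows up to six patients in a cohort after one event. A second event at the fourth patient then has probability 3p²q² = 0.00115 / 0.0243 / 0.0768, with 9 − 7 = 2 left. A second event at the fifth leaves 1 and at the sixth leaves none. These cases do not arise if the one-event entry in Table 2 for the 14-day cohort, "Add additional patients to Cohort 1", is followed instead.

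**21-day cohort**, after three event-free patients at each earlier duration. Both of the first two: p² = 0.0004 / 0.010 / 0.040, with 9 − 8 = 1 left.

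**For scale.** The chance of two or more wound problems among all nine treated patients is 1 − q⁹ − 9pq⁸ = 1.3% / 22.5% / 56.4%.

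**The case against.** The strongest reply is that the two rules work at different levels. Table 2 sets the duration while the study runs, and the termination clauses decide whether it runs at all. Those clauses are mandatory and appear in four places, and a terminated study has no cohort to return to. The Table 2 heading also keeps a purpose if termination prevails, because mixed pairs and two infections still lead to a step back. This stands, and it is why termination is the natural reading. It does not correct the table, whose heading names wound-healing problems with no limit on the combination.

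A second reply is that the text of 5.2 speaks of effects during the treatment period, whereas wound problems follow surgery. That weakens the text as support. The overlap then rests on Table 2, which names wound healing expressly.

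A third reply is oversight. Under Medical Monitoring in 6.5, safety data go to the DSMB after every three patients and on any possibly related serious adverse event. This makes continued dosing unlikely, but it does not tell the board which rule governs.

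A reader might infer from 6.5 that termination is discretionary, since a decision on termination follows any wound breakdown, dehiscence or infection. The documents do not support this. That sentence applies from a single event, so it is a safeguard below the two-case threshold and does not weaken the mandatory rule.

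A reader might also infer that the 7-day cohort has no instruction, because no level precedes it. The cohort 1 result cells are blank in the available text and may have been lost when the table was read, and possibly related serious adverse events go to the DSMB in any case. That point is not made here.

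**Conclusion.** The point holds in a narrow form and is minor. For two primary wound-healing problems in the same 14- or 21-day cohort, the result stated in Table 2 contradicts the termination rule and is wrong. Other pairs of serious adverse events within a cohort do not conflict.

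A reader might go further and conclude that the plan permits dosing beyond its own stopping limit. It does not: four mandatory clauses terminate the study, and only the table is out of step.

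The chance of meeting the overlap in the first three 14-day patients is about 0.12% at the documented 2% ceiling. The 2.8% and 10.4% figures rest on assumed rates of 10% and 20%. At most 3 patients would be left to dose, or 4 in the earliest case. All these figures assume independent patients, three event-free 7-day patients, and no other serious adverse events.

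**What to change.** Add one sentence to 5.2 and a note to Table 2: the termination rule (two primary wound-healing cases or three serious infections, cumulative over all cohorts) is applied first and overrides the cohort rule. Limit the two-event column of Table 2 to combinations of serious adverse events below that threshold. The same sentence settles the order if three serious infections occur in one cohort.

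The cost is amendment wording only, with no added visits, patients or analyses.
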